2.0 Background

Obesity in the United States is a public health problem among all racial/ethnic groups, ages, genders, and geographic areas. However, compared to their counterparts, the prevalence of obesity among AA adults is higher (47.8% vs. 34.9%)¹. Likewise, AA youth between the ages of 10 to 17 are more likely to be obese than their Hispanic, White and Asian counterparts (23.8% vs 21.4% vs 12.0% vs 8.1%)². Further impacting these disparities and their corresponding health risks, adherence to physical activity (PA) guidelines is suboptimal, especially among AA families with adolescents^{3,4}. In South Carolina, the site of the proposed study, the obesity rate among youth is 20.1%, ranking third in the nation². The short-term health implications resulting from adolescent obesity include an increased risk for asthma and other cardiometabolic disorders⁵⁻¹³. The annual economic impact of direct outpatient and inpatient costs of childhood obesity are estimated to be \$14.1 billion¹⁴ and \$237.6 million¹⁵, respectively. The long-term effect of obesity for adolescents is their increased chances as an adult for persistent obesity, cardiovascular conditions, Type 2 diabetes, morbidity, and mortality^{8,10,13}. Since adolescent obesity is a risk factor for adult obesity, there is need for prevention at an early age to reduce the high medical and productivity costs. In the United States, \$173 billion is spent annually on medical costs pertaining to adult obesity¹⁶.

Treatment options for adolescent obesity include lifestyle modification, behavioral interventions, pharmacological treatment, and bariatric surgery (BS). However, compared to eight pharmacological options for adults, only three have been approved by the FDA for adolescent obesity, primarily because of a lack of evidence. BS is an option for adolescents with severe obesity and/or serious comorbid conditions^{13,17,18}, but there is a lack of data on its long-term safety and effectiveness^{13,17}. Further, obese children and adolescents living in rural areas are less likely to undergo an evaluation for BS¹⁹. Even with recent advances in BS and pharmacologic treatments, the first line of treatment for adolescent obesity continues to be lifestyle modifications in conjunction²⁰ with BS^{19,21,22}, medications²³, and multicomponent behavioral interventions^{24,25}. Moreover, parental involvement is also associated with the effectiveness of weight loss interventions for obese children^{26-29, 19-22}. For African American Adolescents with Obesity (AAAOs) and their family, access to intensive behavioral interventions is a challenge, especially for those living in rural areas who face limited options for healthcare providers³⁰ specializing in these interventions³¹ or inadequate transportation^{31,32}. In addition, the types of interventions for AAAO do not address the motivational factors that interfere with adherence to evidence-based recommendations. Treatment studies involving AAs have reported attrition rates ranging from 27% to 55%³³⁻³⁶. FIT Families (HL155793), the basis for the DWN-FIT, addresses access issues through an at-home evidence-based intervention and the problems with adherence and motivational factors through Motivational Interviewing (MI) delivered by Community Healthcare Workers (CHWs) and Contingency Management (CM), increasing caregiver participation by monitoring the adolescent's implementation of evidence-based cognitive behavioral skills and physical activity (PA), and modeling these skills by self-monitoring (SM) of their own diet and exercise and increasing their own PA. We propose to expand the intervention components of FIT Families by including social support (SS), which has been cited as a key element in treatment adherence³⁷⁻⁴¹ when disease management requires significant lifestyle modifications. While several studies have demonstrated a lack of moderator effects of gender on SS, we hypothesize that age (particularly children and adolescents) and race may be important moderators, a hypothesis supported by a recent review by Duh-Leong et al.⁴² who framed social support outcomes in the context of a three-component social capital construct.

Through the translation and evaluation of the FIT Families components, we will add to the limited research investigating digital interventions targeting AAAO and their caregivers. Additionally, the realization of DWN will enable future research and development of evidence-based digital interventions targeting AAAO. Successful outcomes of the proposed work will provide the evidence needed to support a larger, more comprehensive randomized clinical trial and commercialization of DWN (Phase II).

This study aims to expand the FIT Families intervention through a digital adaptation using mobile technology and automation to increase AAAO and caregiver (participants) engagement and adherence. Specifically, the DWN platform will assist participants in understanding, tracking and completing intervention components, delivering educational content, and collecting information from external sources such as wearables (i.e. Fitbit smart watch). Through the mobile app, participants will receive weekly Cognitive Behavioral Skills Training (CBST) modules providing educational content in a video format on cognitive behavioral skills that addresses factors that commonly contribute to poor adherence to healthy behavior recommendations. These modules will also include demonstrations of the weekly PA workouts to be performed by the participants.

Accompanying the video modules are the mobile app's self-monitoring (SM) and the PA features. The SM feature consists of a conversational interface that conducts periodic assessments with the participants to assist them in tracking their daily implementation of the cognitive behavioral skills learned. The PA feature retrieves and tracks the step counts and workout sessions of the participants by collecting data from their wearable devices (Fitbits). Data from the SM and PA are collected by DWN, and an automated analysis is conducted comparing them to the goals set by the participants and the CHW. Based on this analysis, the CM feature provides a monetary incentive (disbursed weekly) to the AAAO and the caregiver for adhering to intervention components. Through the mobile app interface, DWN also provides textual and visual feedback to the AAAO and the caregiver as they progress through the intervention. From the mobile app interface, the caregiver can review and comment through the messaging feature on the adolescent's progress. In one of the treatment conditions detailed below, DWN will deliver semi-automated encouraging messages to the participants during the intervention through the Social Support (SS) feature, which provides feedback on the participants' progress to their supporter (family member or friend). From the mobile app interface, the supporter reviews and provides encouraging messages on the participants' progress.

The CHWs will meet weekly with their participants via video conference (telehealth) to deliver the Motivational Interviewing needed. Between the weekly sessions the CHWs monitor the participants' adherence to the intervention using the web-based dashboard. If they are not doing so, the DWN notifies the CHW, who has the option to reach out directly to the participants through our messaging feature.

Preliminary Studies:

FIT Families The NHLBI/NICHD Center Grant (U01HL097889; [name], consultant in this work) proposed to translate basic behavioral science into novel obesity interventions, targeting the basic science of motivation and communication, and skills training for AAAO using phased intervention development (ORBIT) and a novel design (SMART) to test multiple components that were optimized and are now being tested in a NHLBI-funded clinical trial (R33 HL155793).

Digital Wellness Nurse (DWN): The DWN virtual care platform is based on a research project begun at Clemson University by investigators [name], [name] and [name]. We have developed and evaluated the self-monitoring feature of the DWN as part of COVID-19 Pilot Study using 25 participants. During the 3 months of the study, 149 assessments were successfully submitted without error or loss of data. Besides demonstrating self-monitoring, the study also highlighted the implementation of a secure and privacy-based cloud platform including the following mechanisms: data are encrypted on transit and at rest; personal identifiable information (PII) and personal health information (PHI) are stored in two separate cloud storage spaces; the PHI is only linked to users by a unique id that is randomly generated; and tokens are used to authenticate the participants. Through a series of system tests, we have also formally evaluated the scalability of our cloud resource, finding that the DWN platform can handle 500 simultaneous service requests from users, more than the amount of cloud resource needed to conduct Phase 1 studies.

3.0 Intervention to be studied

The two interventions to be studied are: 1) DWN-FIT and 2) DWN-FIT_Social Support.

Components of Digital Intervention for DWN-FIT and DWN-FIT_Social Support:

Cognitive Behavioral Skills Training (CBST) Video Modules: Every week a group of 3 - 5 videos will be made available to the AAAO and their caregiver, no longer than 5-minutes in length. Videos are based on the mandatory modules used within FIT Families. These instructional modules will be translated to scripts and scenes with the guidance of [name] (Consultant and FIT Families Co-I).

The proposed schedule is as follows:

- Week 0 – DWN-FIT Orientation and Getting Started on the Mobile App
- Weeks 1-2 – physical activity (PA) education
- W3-4 – nutrition education
- W5-6 - parenting strategies (only available to caregiver) and self-monitoring (SM)
- W7-8 - environmental control of nutrition and PA
- W9-10 - managing hunger
- W11-12 - managing cravings

Self-Monitoring (SM) Assessments: Throughout the study, participants will complete assessments via the conversational interface of the mobile app. At the beginning of the intervention (T0), participants will complete a baseline assessment focused on their current engagement in- and perception of-healthy behaviors (eating habits and physical activity level). This assessment will be adapted from the Patient Health Engagement (PHE) Scale⁴⁸. The same questions regarding patient engagement will also be asked at each assessment time point (T1 – T3). The DWN will prompt the participants daily to use the SM feature of the mobile app to complete an assessment that will determine their daily implementation of the physical activity tasks and cognitive behavioral skills learned. For example, participants will be asked to complete a food log that documents the amounts of fruits and vegetables, junk food, water, protein, and whole grains consumed each day. These food types and their suggested quantities are detailed in the nutrition education learning modules. The DWN will also conduct weekly assessments, initially only asking participants to weigh themselves and record their body fat. As the intervention progresses, in collaboration with the CHW they will also be asked to set their weekly treatment goals and reflect on their goals from the past week (barriers that prevent them from reaching their goals and if they need to modify their goals). As a part of SM component, the caregiver and CHW are notified when the AAAO submits or misses submitting an assessment. Once an assessment is submitted, the caregiver reviews the adolescent's progress. If the AAAO does not submit the required assessment or if the caregiver does not review one, the CHW is alerted, and they have the option to reach out directly to the participants through the messaging feature.

Physical Activity (PA): In W1, participants begin wearing the Fitbit wearable provided and set their step count goals during the weekly assessment. In addition, four CBST video categories will demonstrate the independent PA workouts the participants will perform weekly: 1) Warm-up (5 minutes); 2) High intensity interval training for cardiovascular fitness (20 minutes); 3) Resistance band and body weight resistance training (20 min); and 4) Cool down with yoga stretches (5 minutes). Participants will perform these PA workouts while wearing their Fitbit. The number of client workouts during the week depends on their PA goals set during the weekly assessment. The DWN provides textual and visual feedback on the client's step count and workout sessions. As a part of the PA component of the intervention, the caregiver and CHW are notified when the AAAO receives this feedback, at which time the former reviews the adolescent's progress. If the AAAO does not meet their PA goals or if the caregiver does not review the feedback, the CHW is alerted, and they have the option to reach out directly to the participants through the messaging feature. The AAAO and caregiver will receive Fitbit Inspire 3s, resistance bands, a yoga mat, and a Body Composition Scale as a part of the study. The equipment will be returned to the investigator at the end of the intervention phase.

Contingency Management (CM): The CM feature provides financial incentives to attend sessions and to encourage families to meet the following weekly goals (\$10 per goal): step count, nutrition SM, CBST education, and PA participation. Caregivers have the opportunity to receive bonus incentives (\$50 for completion over three consecutive weeks, maximum 3 bonuses over study duration) for reviewing the AAAO's PA participation and nutrition SM entries. AAAOs may also receive bonus incentives using the same pay structure (\$50) for every four consecutive weeks of at least a one-pound weight reduction. Session attendance (telehealth visit with CHW) is also incentivized at \$50 per session for the AAAO and caregiver, individually. CM

goals will be released along with the accompanying CBST material so that families have adequate knowledge to apply the prescribed strategies. Successful attendance and completion of all goals (including bonuses) over the 12-week period results in a total value of \$1230. Incentives will be disbursed as reloadable debit cards (ClinCard).

Video Conferencing (Telehealth): Weekly telehealth sessions lasting approximately 45-minutes to 1 hour are delivered to the participants by the CHW through a video chat interface in the DWN mobile application, including 1) review of SM goals; 2) review of PA steps and calories burned; 3) Goal setting based on assessments and learning modules; and 4) review of CBST learning modules using evidence-based steps for skill acquisition (discussion of rationale, modeling of skill, caregiver and AAAO behavioral rehearsal of skill, feedback), and caregiver and AAAO develop implementation plans for between session skills practice.

DWN-FIT_Social Support (SS) intervention:

Participants randomly selected for the SS condition of the DWN-FIT will receive all of the components of the DWN-FIT intervention as described above. In addition, DWN-FIT_SS families will be asked to invite a family member/friend to serve as the supporter. Once consented and accepted as a research participant, the supporter will be compensated \$60 each week of the 12-week study period for providing encouraging messages to both the caregiver and AAAO. The supporter will be instructed by the research assistant to download the application. The supporter is automatically prompted at the following points: one day after release of CBST educational modules; twice per week for PA; and at the beginning, middle, and end of week to encourage SM and follow-up by caregivers.

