Methods: This aim follows two conditions (DWN-FIT vs DWN-FIT_Social Support [SS]) x 4 time (T0: baseline, T1: 1-month follow-up, T2: 2-month follow-up, and T3: 3-month end of treatment), with random assignment of 16 families (caregivers/AAAO) to one of the two treatment conditions. The proposed 3-month treatment period is too short to assess the feasibility of this digital treatment with respect to weight loss measurements (secondary outcomes), so instead we will assess feasibility of this approach based on the development of healthy behaviors (primary outcomes) that have been shown to lead to sustainable weight loss over time. Primary outcomes will be measured after each session (weekly) through the data recorded by the DWN app. These primary measures consist of the following measurements via the DWN app: step count, PA and PA video views, frequency and consistency of nutrition SM, messaging read and response rates, frequency and consistency of CBST education participation, telehealth session attendance, and CM rewards. In both treatment conditions, we will determine correlation between these measures and our measures of engagement and adherence. We will also determine the effect of semi-automated SS on each of the measures by comparing outcomes from each treatment group (DWN-FIT vs DWN-FIT_SS). Caregiver and AAAO percent

overweight and body-mass index (BMI) will serve as secondary outcome measures and will be collected each week via a provided digital scale. These secondary outcomes will be used to build preliminary data for a future full time-course (6-month or greater) randomized clinical trial (RCT).

Measures: We will measure **engagement** through the delivery of the 9-item Patient Health Engagement (PHE)⁴⁸ survey. The PHE is used to determine the degree to which patients are engaged in their own health and describes the patient's ability to manage their own health. PHE has been validated in other work, but a sample size large enough to meet this threshold is outside the scope of this study. The PHE outcomes gathered here will be used as preliminary data for future studies. The PHE survey will be taken via the DWN app at each time point, T0-T3. We will measure **adherence** through comparing the prescribed tasks against the task completed, raw counts (video views, SM entries, PA participation), by each set of participants. We will explore how SS is correlated with adherence to the prescribed treatment.

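### Adolescent weight, the basis of two secondary outcomes, is self-measured at home with no stated check, while adolescents are paid when it falls

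*Protocol*

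**What the plan says.** Four parts of the protocol bear on this.

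- **How weight is obtained.** Under Self-Monitoring Assessments in section 3.0, "participants will complete assessments via the conversational interface of the mobile app". On the weekly ones it says: "The DWN will also conduct weekly assessments, initially only asking participants to weigh themselves and record their body fat".
- **What is paid.** Under Contingency Management in section 3.0: "AAAOs may also receive bonus incentives using the same pay structure (\$50) for every four consecutive weeks of at least a one-pound weight reduction". The weekly $10 goals are "step count, nutrition SM, CBST education, and PA participation", so neither weight nor body fat is among them. The caregiver bonus is "for reviewing the AAAO's PA participation and nutrition SM entries".
- **What the weight is used for.** In section 9.0, Aim 1 Methods, the percent "overweight and body-mass index (BMI) will serve as secondary outcome measures and will be collected each week via a provided digital scale". They are meant as preliminary data for a later randomised trial.
- **What triggers payment.** Section 2.0 says that the platform analyses self-monitoring and physical-activity data automatically and that the incentive follows from that analysis.

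Section 6.0 places the whole study on the virtual platform. The measures table in section 9.0 names the Fitbit as a data source for Fitbit data, but lists only youth and caregivers for percent body fat. The CHW's weekly note in that table has a line for percent body fat and none for weight.

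**The concern.** The adolescent reads the scale, supplies the value and is paid if the value goes down. A falling series could then reflect true loss, the best of several weighings, or a number simply entered, and nothing in the described data would separate these. An error of this kind does not average out, because it runs towards loss.

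Two uses of the data are exposed. One is the change in adolescent BMI and percent overweight over the 12 weeks, which the next trial would draw on. The other is the link between engagement and weight loss that section 1.0 expects: adolescents who respond most to incentives may both use the app more and report more favourable weights. In addition, section 9.0 lists contingency-management rewards among the primary measures, and that total would include the weight bonus.

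**Working it through.** **Step 1: reproduce the stated maximum.** Inputs from section 3.0: 12 weeks, four goals at $10 a week, one session a week at $50 "for the AAAO and caregiver, individually", and $50 bonuses.

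- Goals: 12 x 4 x $10 = $480
- Sessions: 12 x $50 = $600
- Adolescent weight bonuses: 12 / 4 = 3, and 3 x $50 = $150
- Total: 480 + 600 + 150 = $1230, as stated

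Without the weight bonuses the adolescent's total would be $1080. The plan's own figure therefore counts three of them, and the share that depends on recorded weight is 150 / 1230 = 12.2%.

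**Step 2: trace the weight from scale to payment and outcome.**

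| Link | What the protocol gives |
|---|---|
| Measurement | Self-weighing at home on a supplied scale (3.0) |
| Transfer to the database | Not stated for weight; device retrieval is described only for Fitbit steps and workouts (2.0) |
| Independent reading | None described; screening height and weight are self-reported and confirmed by phone (7.0) |
| Session content | Goals, activity and learning modules; no weigh-in (3.0, 9.0) |
| CHW note | Percent body fat, not weight (9.0 table) |
| Payment trigger | Follows the automated analysis of self-monitoring data (2.0); the record used for the weight bonus is not named (3.0) |

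The weekly weigh-in is part of self-monitoring, so the natural reading is that the participant's own weight record drives the bonus.

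**Step 3: how large could the error be?** The rule can be read as one pound per four-week block (3 x 1 = 3 lb) or one pound in each week (12 x 1 = 12 lb). With 1 lb = 0.4536 kg, the apparent fall in BMI is weight / height squared. Heights are not in the protocol, so 1.5 to 1.8 m is assumed.

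| Reading | kg | at 1.5 m (divide by 2.25) | at 1.8 m (divide by 3.24) |
|---|---|---|---|
| 3 lb | 1.361 | 0.60 kg/m2 | 0.42 kg/m2 |
| 12 lb | 5.443 | 2.42 kg/m2 | 1.68 kg/m2 |

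These figures show what one adolescent would have to misreport to earn every bonus. They do not estimate the bias in the study.

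**Step 4: who has the motive?** The bonus covers the weight of 16 of the 32 family participants (section 5.0). Caregivers are not paid for weight, and nobody is paid for body fat.

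**The case against.** The strongest reply is that the capture route is unspecified rather than known to be manual. Section 9.0 says the data come by way of a digital scale, which does not rule out automatic upload. Section 11.0 lists body fat apart from questionnaire responses. In section 3.0 the verb for recording is attached to body fat, not weight. This stands as far as it goes. If the scale uploads directly, one sentence in the protocol would largely settle the matter. As written, no such sentence exists.

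The protocol also has some oversight. Caregiver and CHW are told of each submission, and the caregiver reviews the adolescent's progress. But nobody is asked to see the scale, and the one related line in the CHW note concerns body fat, without saying whether the value is observed or copied.

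Two stronger readings are tempting and are not supported:

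- **That body fat, or caregiver weight, is also distorted by payment.** No payment depends on either. Body fat shares the weakness of self-entry, but not the motive.
- **That the social-support comparison is biased.** Both arms receive the same contingency management, so bias needs misreporting that differs by arm. Supporters are given feedback on progress, but no section says that they see weight.

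It is also fair to say that section 9.0 treats weight as secondary and calls three months too short for judging feasibility by weight loss. The behavioural measures are untouched, apart from the rewards total.

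**Conclusion.** The point holds for adolescent weight, and so for adolescent BMI and percent overweight. These outcomes are self-measured, rewarded when they fall, and have no stated verification. Change within groups and its correlation with engagement or adherence could be shifted towards loss. The amount at stake is $150 of $1230 per adolescent. The illustrative error is 0.42 to 0.60 kg/m2 if the rule means a pound per four-week block, or 1.7 to 2.4 kg/m2 if it means a pound a week.

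The conclusion rests on the self-entered weight being the one that triggers payment, which sections 2.0 and 3.0 imply but do not state. The BMI figures rest on assumed heights and on every bonus being earned by false values. The point does not overturn the behavioural feasibility aims. It limits what the weight data can contribute to the later trial, and it is cheap to put right.

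**What to change.** In section 3.0 (Self-Monitoring), section 9.0 (Aim 1 Methods) and the measures table:

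1. Define the outcome weight as the reading uploaded directly from the supplied scale. If the scale cannot upload, define it as the scale display shown to the CHW at the existing weekly video session, with only the display in view.
2. Add a weight line to the CHW note.
3. State that the existing bonus is determined from that verified record.
4. Flag app-only entries as unverified, and report the weight outcomes with and without them.

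**Cost.** Protocol wording, one extra field and about a minute per session, with no new staff or visits. There are three downsides. Showing the scale may embarrass some adolescents, and section 12.0 already names embarrassment as a study risk. It might also affect session attendance, which is itself a primary measure in section 9.0; direct upload avoids both. With the display route, a missed session leaves no verified weight for that week, so the protocol must also say how such a week counts towards the four consecutive weeks of the bonus.

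### A T0 baseline is named, but the text starts Fitbit wear in the week step goals and activity education begin, and the schedule contradicts itself on a week-0 step count

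*Protocol*

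**What the plan says.** Section 9.0 (Aim 1, Methods) crosses two conditions with four times: "x 4 time (T0: baseline, T1: 1-month follow-up, T2: 2-month follow-up, and T3: 3-month end of treatment". The same paragraph lists step count first among the primary measures and adds: "Primary outcomes will be measured after each session (weekly) through the data recorded by the DWN app".

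Section 2.0 says that step counts are retrieved from the Fitbits. Section 3.0 (Physical Activity) fixes when wear starts: "In W1, participants begin wearing the Fitbit wearable provided and set their step count goals during the weekly assessment". In the module schedule of section 3.0, weeks 1-2 cover "physical activity (PA) education", and week 0 holds only "DWN-FIT Orientation and Getting Started on the Mobile App". The baseline that section 3.0 describes is a questionnaire: "At the beginning of the intervention (T0), participants will complete a baseline assessment", adapted from the PHE scale. On body composition it says: "The DWN will also conduct weekly assessments, initially only asking participants to weigh themselves and record their body fat".

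The schedule table closing section 9.0 has columns for weeks 0 to 12 and one for weeks 13-16. Steps and calories are ticked at week 0. Both Fitbit rows and the body-fat row are blank there and start at week 1.

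Section 10.0 plans Pearson correlations and an independent two-sample t-test between arms at alpha 0.05. Section 5.0 gives 16 families, 8 of them in the social support arm.

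**The concern.** A design with a named baseline and step count as a primary measure would normally record steps before treatment acts on them. On the text, the first Fitbit data come in the week when step goals are set and activity education begins. Meeting the step goal also earns a weekly payment, and goals are released with the matching module, so the incentive may apply from that week too.

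The table does not settle the matter, because its week-0 step and calorie ticks have no device behind them in its own Fitbit rows. Staff cannot follow both.

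At stake is a value that cannot be recovered. A later analysis plan can choose a covariate, but it cannot create a measurement that was never taken. The study is meant to supply evidence for a larger randomised trial, where an untreated step level and its correlation with later steps would be useful.

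**Working it through.** **Timing, side by side**

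| Item | Week 0 | Week 1 |
|---|---|---|
| Fitbit wear (section 3.0) | not mentioned | begins |
| Step goals (section 3.0) | not mentioned | set |
| Education (section 3.0) | orientation | physical activity |
| Fitbit rows, two (schedule) | blank | ticked |
| Steps and calories rows (schedule) | ticked | ticked |
| % body fat row (schedule) | blank | ticked |

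The extracted columns look reliable where the text fixes the timing. The usability scale falls at week 6 (text: midpoint), the needs post-survey at week 12 (text: after completion), and the focus groups at 13-16 (text: after W12).

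So the text and the Fitbit rows give no week-0 step count, while the step and calorie rows require one. Which holds depends on which passage governs.

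**Chance imbalance.** With 8 families per arm and one value per family, the standard error of the arm difference in a baseline mean is sqrt(1/8 + 1/8) = 0.50 SD. For normal values:
- P(|difference| > 0.5 SD) = P(|Z| > 1) = 0.317
- P(|difference| > 1 SD) = P(|Z| > 2) = 0.046

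These rates hold for any covariate at this size. Without a T0 step count the imbalance simply cannot be seen.

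**Precision, illustration only.** The protocol states no power, effect size, SD or correlation, so there is no figure of its own to reproduce. Assumed: two-sided alpha 0.05, 80% power, 8 v 8.

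Unadjusted t-test, 14 df: the noncentrality needed is 3.013, so the detectable difference is 3.013 × 0.50 = 1.51 SD.

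Adjusted for baseline (ANCOVA), 13 df: the noncentrality needed is 3.031. The standard error is 0.50 × sqrt(1 − ρ²) × sqrt(1 + 1/12), where the last factor allows for expected covariate imbalance.

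| Assumed ρ | Standard error (SD) | Detectable difference (SD) |
|---|---|---|
| 0.3 | 0.496 | 1.50 |
| 0.5 | 0.451 | 1.37 |
| 0.7 | 0.372 | 1.13 |
| 0.8 | 0.312 | 0.95 |

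Break-even is where 3.031 × sqrt(1 − ρ²) × sqrt(13/12) = 3.013, which gives ρ = 0.30. The simpler formula 1.507 × sqrt(1 − ρ²) gives 1.30, 1.08 and 0.90 SD at 0.5, 0.7 and 0.8. It ignores the lost degree of freedom and the covariate imbalance, so the table is the more cautious version.

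**T0 and T3 by instrument.** The needs surveys, placed at T0 and T3 in the text, are ticked at weeks 0 and 12. The PHE, due at T0 to T3, is ticked at weeks 1, 5, 9 and 13-16.

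**The case against.** The strongest reply is that no planned analysis needs a baseline step count. The text ties T0-T3 explicitly to the PHE and describes T0 as a questionnaire. Steps are a weekly measure, and the expected social support effect is a contrast between arms. That stands. A reader might infer that the arm comparison is biased or invalid. It is not: randomisation protects the t-test, and its alpha already allows for chance imbalance.

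Second, the loss is conditional. A reader might infer that step baselines are definitely absent. The documents do not support this: if the week-0 ticks govern, the value is recorded, and the Fitbits are mailed when the first session is scheduled. Section 3.0 also says weekly assessments at first ask only for weight and body fat, so some wear before goal setting is possible, though not secured. The week-1 body-fat reading may likewise serve as T0, but nothing places it before the first module or session.

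Third, the device ticks at weeks 13-16 invite the inference that device data are demanded after the equipment has gone back. That reads too much into them. Nearly all weekly rows are ticked in that column, including CHW meetings, food log and messaging, so it looks block-filled. The table header carries an asterisk whose note is not in the text at hand and may define the column. The PHE ticks also fit a four-week spacing (1, 5, 9, 13), so the T3 discrepancy may be a one-week boundary difference.

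Finally, the precision gain rests on assumed correlations, and even the adjusted detectable differences are large. That also stands. It limits the size of the point, not the contradiction.

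**Conclusion.** The point holds as a cheap improvement together with an internal contradiction to resolve. If section 3.0 is followed as written, no step count precedes goal setting and activity education. Change from an untreated value then cannot be described, imbalance at 8 v 8 cannot be seen, and baseline adjustment is impossible. If the week-0 ticks are followed, the value exists, but the text and the Fitbit rows must then be corrected.

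The possible precision gain runs from none at a correlation of about 0.3 to a fall from 1.51 to 0.95 SD at 0.8. It assumes one value per family, normal outcomes and correlations that the protocol does not give. For body composition it applies only if the week-1 reading is not already pre-treatment. Measures of app use, such as video views, messaging, attendance and rewards, have no pre-treatment value and are unaffected.

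The placement of T0 and T3, and the meaning of the weeks 13-16 column, are secondary and editorial.

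**What to change.** 1. Amend the Physical Activity paragraph of section 3.0 so that Fitbit wear and one scale reading start in the existing week 0. They should precede step goals, incentives, the first module, the first CHW session and any in-app step feedback. Feedback matters because it is itself an intervention component. In the social support arm the window should also precede the first supporter message.
2. Tick the Fitbit and body-fat rows at week 0, so that they agree with the step and calorie rows.
3. Label this measurement T0, and use it as a covariate in the arm comparison of steps, physical activity and body composition.
4. Editorial: place T0 and T3 in the same week for the PHE and the needs surveys. Define the weeks 13-16 column and reconcile it with the 12-week period, the 3-month participation and the return of equipment at the end of the intervention phase.

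Cost: a wording and schedule amendment. Equipment must reach families a few days earlier, a few days of wear are added, step feedback must be held back during week 0, and the covariate uses one degree of freedom. No new device or staff is needed.
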